6.2. Definition of Medication Adherence

Data extracted from the Pharmacy Information Network will be used to calculate the Proportion of Days Covered (PDC): “number of days dispensed”/“number of days between prescription renewals” (42,43) using drug data in the ICDC Chronic Disease Repository. Patients with medication supplies to cover $\geq 80\%$ of observed treatment days are considered adherent (44,45).

We will calculate PDC for each participant in the initial 12-month period that they were in the trial for both Statins and ACEi/ARBs. For those switching between statins or agents within the ACE/ARB class, ANY dispensed medication in the class will be included in the analysis.

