**c. Medication Adherence (PDC)**

Adherence to the high-value cardiovascular medications, including Angiotensin Convertase Enzyme (ACE) inhibitors, Angiotensin Receptor Blockers (ARBs), and statins, will be assessed by calculating the proportion of days covered (calculated using the formula below) (sum of days covered in the period of interest (POI))  $\div$  (number of days in the POI)  $\times$  100% (18). Those with 80% or greater PDC are considered adherent, and vice versa.

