4.8. Sample Size

Using the cohort of 170,000 Albertans described above, we estimated the annual event rate for this study reflecting the expected age distribution of enrollees. We found that this cohort of patients at high cardiovascular risk had a 26% risk of myocardial infarction, stroke, death or chronic disease-related hospitalization over a three-year observation period (Appendix VII). However, the endpoint in our primary outcome is not a binary event (many individuals had multiple events during the observation period), and so we have chosen to include recurrent events in our sample size calculation. In our administrative dataset, the rate of the primary outcome (MI, stroke, revascularization, death, or chronic disease-related hospitalization) is 14 per 100 participant years (Appendix VII).

We estimated the sample size required for Poisson regression analysis (31), using the following parameters: an annual event rate of 14 per 100 participant years, a minimal clinically important difference of a 12% relative risk reduction, $\alpha=5\%$, 80% power, allocation ratio of 1:1, average follow up of 3 years and presumed 1 percent per year loss to follow-up (32). The estimated total sample size required for the study was 4714 patients (4667 +1% of individuals who are expected to move out of province during the study) (Appendix VIII). Our sample size calculation assumed that there will not be an important interaction between our two interventions. To verify this assumption, we generated simulations using interactions of 25% and 50%. At both of these levels of interaction, with our current projected sample size, the effect on study power was negligible.

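### Section 6.2 builds PDC from days dispensed with no overlap rule, so overlapping dates can count twice, and the formula differs from SAP section 5.3.c

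*Combined protocol and SAP*

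**What the plan says.** **Combined protocol and SAP, section 6.2.** The measure is named Proportion of Days Covered and is taken from Pharmacy Information Network data.
- Formula: "number of days dispensed”/“number of days between prescription renewals".
- Threshold: supply must cover at least 80% "of observed treatment days are considered adherent".
- Period: "We will calculate PDC for each participant in the initial 12-month period that they were in the trial for both Statins and ACEi/ARBs".
- Switchers: "For those switching between statins or agents within the ACE/ARB class, ANY dispensed medication in the class will be included in the analysis".

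The section does not say whether supply that overlaps in time is added, counted once per date, carried forward or cut off.

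**SAP, section 5.3.c.** The numerator is "sum of days covered in the period of interest (POI"), and the denominator is the number of days in that period. Threshold: "Those with 80% or greater PDC are considered adherent, and vice versa". It names ACE inhibitors, ARBs and statins. It has no rule for switching and does not say whether ACE inhibitors and ARBs are scored as one class.

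**The concern.** Days dispensed and days covered are different quantities. If a new agent is filled before the old supply runs out, or the same agent is refilled early, two fills span the same dates. A sum of days dispensed credits those dates twice; a count of covered days credits them once. Section 6.2 takes its name and threshold wording from the second quantity and its only formula from the first.

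It also points to three denominators: days between renewals, observed treatment days and a 12-month period. SAP section 5.3.c uses another pairing.

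Adherence is a listed secondary outcome (combined document, section 4.4) and is analysed as a binary variable (section 10.5). Two programmers working from these texts could therefore put the same person on opposite sides of the 80% cut. The SAP introduction calls the parent trial's adherence effects modest, so the definition should give one answer per person.

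**Working it through.** **Figures in the plan.** Neither document states a switching rate, a fill length or a misclassification rate, so there is no stated figure to reproduce. The sample size of 4714 rests on the primary event rate and does not depend on the PDC definition.

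**Inputs from the documents.** A 12-month period (section 6.2), taken as 365 days, and an 80% threshold (both documents): 0.80 × 365 = 292 days. Every fill length, fill date and rate below is an assumption.

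**Example 1: one switch.** 90-day fills on day 0 (agent A), day 30 (switch to B), day 120 and day 335.
- Days dispensed, last fill cut at day 365: 90 + 90 + 90 + 30 = 300; 300/365 = 82.2%, adherent.
- Dates covered: days 0 to 209 (210 days) and 335 to 364 (30 days) = 240; 240/365 = 65.8%, not adherent.
- With the denominator of section 6.2, read as first fill to last renewal (335 days): 270/335 = 80.6% dispensed against 210/335 = 62.7% covered. The classification still differs.
- With A's 60 leftover days carried forward and taken before B: days 0 to 269 and 335 to 364 = 300; 82.2% again.

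**Example 2: longer fills.** 100 days of A on day 0, then B for 100 days on days 10 and 110. Dispensed: 300/365 = 82.2%. Dates covered: 210/365 = 57.5%. Carried forward: 82.2%.

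**Example 3: early refill, no switch.** 90-day fills on days 0, 80, 160 and 240. Dispensed: 360/365 = 98.6%. Dates covered, with nothing carried forward: 330/365 = 90.4%. The value moves, but the class does not.

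**Lowest coverage that can pass after one switch.** A fill of L days can overlap the next by at most L − 1 days, so the bound is 292 − (L − 1).

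| Fill length | Days covered | Share of 365 |
|---|---|---|
| 30 days | 263 | 72.1% |
| 90 days | 203 | 55.6% |
| 100 days | 193 | 52.9% |

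**How often, among switchers.** Simulation with 90-day fills, one switch on a random day and exponential refill gaps with mean 15, 30 or 45 days. Share classed adherent: 98%, 82% and 64% by days dispensed; 94%, 64% and 43% by dates covered. The differences are 4, 18 and 21 points.

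**Effect on the comparison if switching is equal in both arms.** Observed adherence = p + (1 − p) × s × m, where p is true adherence, s the share switching and m the share of non-adherent switchers misclassified. Take p = 0.66 and 0.70, so the risk ratio is 1.061.
- s = 0.02, m = 0.25: 0.7015/0.6617 = 1.060.
- s = 0.20, m = 0.50: 0.730/0.694 = 1.052.

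**The case against.** **Double counting is not announced.** Section 6.2 is silent on overlap. Its name for the measure and its threshold wording both fit counting each date once, and the sources it cites for the calculation may do so. This stands in part: double counting is the literal reading, not the only one. But the one explicit formula says "number of days dispensed", and the text does not settle which reading applies.

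**Summing can be right.** If leftover supply is taken before the new supply, the example person really does have 300 days of drug, and 82.2% is correct. This stands. The gap in examples 1 and 2 appears only if old supply is not used after the change. That is a convention the plan has to choose. A plain sum does not choose it, and can pass 100%.

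**Including any agent of the class is sound.** This stands. It keeps people who change agent from being called non-adherent to a class they still take. The fault is the numerator and the missing overlap rule.

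**SAP section 5.3.c already uses days covered.** True, and it is the better base. It still says nothing on pooling or leftover supply.

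**The parent-trial adherence results are already reported** (SAP introduction), so new wording cannot guide that analysis. This stands for the completed analysis. The definition actually used there can still be stated, and the secondary analysis can still be specified.

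A reader might infer two stronger points that the documents do not support:
- *The error favours one arm.* The personalized recommendations go to patients not on guideline-recommended therapy at baseline (combined document, section 4.2), so their direct effect is starting a drug, not changing agent within a class. Nothing says that switching or early refills differ by arm.
- *The two documents score an ACE inhibitor to ARB switcher in opposite directions.* Section 5.3.c lists the drugs but does not say that each is scored alone. The SAP pairs them in its introduction, rationale and subgroup list (section 7.4, item i).

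**Conclusion.** The point holds as a defect of definition. The formula written in section 6.2 departs from the measure it names and from SAP section 5.3.c in both numerator and denominator. Taken literally, it counts overlapping dates twice, and a person with 65.8% of days covered can pass the 80% cut at 82.2%. What is counted twice is calendar days; each dispensed supply enters only once.

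The size for the trial cannot be established from the documents. The gap of 4 to 21 points concerns switchers only and rests on assumed fills and gaps, with no carry-forward. With equal switching in both arms, the assumed risk ratio moves from 1.061 to no lower than 1.052. Unequal switching has no documented basis.

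This should be corrected because the fix is cheap and the outcome is a binary cut. It is no ground for saying that the reported adherence effects are biased.

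**What to change.** Use one definition in section 6.2 and SAP section 5.3.c:

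1. **Numerator:** calendar days in the fixed period on which at least one agent of the class is available, each day counted once, with PDC capped at 100%.
2. **Denominator:** days in that same fixed period, replacing days between renewals and observed treatment days.
3. **Classes:** statins as one class; ACE inhibitors and ARBs pooled as one. Keep the any-agent rule and state it in section 5.3.c.
4. **Leftover supply:** state the convention at a switch (cut off at the first fill of the new agent, or carry forward) and report the other as a sensitivity analysis. State the rule for early refills of the same agent too.
5. **Completed analysis:** state which formula was used for the reported parent-trial adherence results.

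The cost is a change of wording and a day-by-day recalculation on dispensing data already held; the sample size is unaffected. Adherence percentages may become slightly lower. Cutting off old supply undercounts people who finish it or return to it, and carrying it forward credits people who discarded it, which is why both should be shown.

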6.3. Definition of Quality of Life

The Canadian-specific EQ5D index score will be the primary quality of life measure. For patients who die during the study, subsequent index scores will be given a score of 0, consistent with usual EQ-5D convention (scale is anchored at zero and 1, with zero being dead and 1 being perfect health).

Mixed models will be used to compare EQ-5D index scores over time between the treatment groups for each intervention.

In secondary analyses of EQ-5D index scores, to assess the impact of missing data, we will consider two alternate methods using imputation. Firstly, we will impute missing variables using multiple imputation as noted in section 10.3. We will then use this data to compare the area under the curve of index scores across each intervention group (equivalent to comparing a “QALY” profile for each participant). Secondly, we will use last observation carried forward to impute missing values, and then similarly compare the area under the curve of index scores. Both approaches will test the impact of missingness of data.

7. Trial Population

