4.6. Timing of outcomes as assessments

The primary outcome data was ascertained through administrative health data held within the province of Alberta, including linked datasets such as: laboratory data, pharmacy dispensation data, acute care data, outpatient physician claims data, and demographic data. Participants were followed for a minimum of 2.5 years from the time of randomization through until March 30, 2021. This data will be available as of early 2022.

Self-reported outcome measures were obtained via electronic and paper-based surveys which were sent to participants 6-, 18-, and 33-months after randomization.

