5.1. Confidence Intervals and P-values

In all our analyses, we will calculate 95% Confidence intervals around all point estimates and will calculate p-values using appropriate statistical tests. We will consider our alpha value to be 0.05.

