10.3. Handling Missing Data

Given that our primary outcome is determined using administrative data, we anticipate minimal missing data for our principal analysis. Therefore, we will use intention-to-treat principles for this analysis.

However, our secondary outcomes rely on self-reported data and therefore there may be considerable missing data points. For the analyses of these outcomes, we will undertake the following procedures for handling missing data:

We will first check the degree and patterns of missingness in the data, based on which we will consider optimal ways of handling missing data to minimise the bias potential. In the presence of missing at random (MAR) given the observed data, we will use methods such as multiple imputation or full information direct maximum likelihood to analyze the missing data.

If the MAR assumption is in doubt, then we will also conduct sensitivity analyses to assess the potential impact that missing not at random (MNAR) may have on the analytic results. Exploration of the sensitivity of conclusion to the MAR assumption may include models which allow for missingness that is not random. These models will include variables that we find to be related to missingness as well as those potentially related to the outcome (including age, sex, baseline medication adherence, comorbidities, household income).

If loss to follow-up is related to the level of the outcome being analyzed, then results obtained under the assumption of independent loss to follow-up may be biased; and in this situation, we will investigate the magnitude of this problem by using measurements taken at previous visits to predict loss to follow-up, and include variables that are determined to predict loss to follow-up in our predictive models in order to satisfy the conditions for the data to be considered MAR, with maximum likelihood techniques being used to estimate parameters. If necessary, we will also examine other approaches in consideration of how robust the results will be and whether they provide appropriately conservative estimates for the outcome analyses.

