10.9. Sensitivity Analyses

Sensitivity analyses will be conducted as follows:

- Excluding those who have admissions/costs in the top 1% of all participants
- Excluding participants who resided in the same household as another participant.
- We will also conduct a complete case analysis to examine the effects of the missing data, where relevant (ie. Self-reported outcomes).

11. Interaction between intervention arms

Given the factorial design of the trial, we will assess for multiplicative interaction. Because each of our two interventions was designed to address very different patient barriers to

medication adherence (financial barriers vs. Knowledge/motivation), we don't anticipate major multiplicative interaction effects.

12. Health Economic Analysis

The primary outcome will be mean total 3-year in-study health care costs for patients receiving copayment elimination (or not) and those receiving MOXIE (or not), adjusting for co-intervention received. We will include costs for hospitalization and ED visits, physician claims (specialist and primary care physician visit and procedure billing costs), prescription medications (including those subject and not subject to copayment elimination), nonphysician ambulatory costs (day medicine and day surgery clinics), and outpatient diagnostic imaging and laboratory costs. The total costs will be calculated as the sum of these costs. Alberta Health uses Canadian Institute of Health Information case-mix grouper methods to estimate hospital costs and ambulatory-case costing methods to estimate outpatient costs.

Physician claims will be based on the amount paid by Alberta Health. The cost of medications will be estimated by combining a database containing a comprehensive list of medications dispensed to all Alberta residents with a price list from Alberta Blue Cross, including dispensing fee. Diagnostic imaging and laboratory costs will be based on estimates provided by Alberta Health Services. All costs will be reported in 2021 Canadian dollars.

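### Section 6.3 scores almost every death but only those living participants who return a survey, so the EQ-5D mean falls below the value that scoring death as 0 is meant to give, unless the living are modelled separately

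*Combined protocol and SAP*

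**What the plan says.** All references are to the combined protocol and SAP. EQ-5D is a secondary outcome (4.4).

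- **Scoring and model.** Section 6.3: "For patients who die during the study, subsequent index scores will be given a score of 0". It then names the comparison: "Mixed models will be used to compare EQ-5D index scores over time between the treatment groups for each intervention". No covariance structure is given. Two imputation-based comparisons of area under the curve, one by multiple imputation and one by last observation carried forward (LOCF), are secondary.
- **A second model.** Section 10.5 names linear regression for the same index score.
- **Where living scores come from.** Section 4.6: "Self-reported outcome measures were obtained via electronic and paper-based surveys which were sent to participants 6-, 18-, and 33-months after randomization". Section 10.3 warns that "our secondary outcomes rely on self-reported data and therefore there may be considerable missing data points".
- **Where deaths come from.** Section 6.3 does not say, but the only source described is administrative. Section 6.1 takes death from Vital Statistics. Section 10.4 follows people in administrative records until they die or leave the province. Section 9.1 keeps administrative data after withdrawal, except for people who asked for all their data to be removed.
- **Missing data.** Sections 9.1 and 10.3 plan multiple imputation, or full-information maximum likelihood, under missing at random. Vital status is not among the predictors listed in 10.3, and nothing limits imputation to the living. Section 10.9 adds: "We will also conduct a complete case analysis to examine the effects of the missing data".

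**The concern.** Two sources with different coverage feed one variable. At each wave a dead participant contributes a 0 with near certainty, while a living participant contributes a score only on response. Being scored thus depends on vital status, and so on the value itself. Missing at random fails for the combined score given the observed scores alone, even if non-response among survivors is completely random.

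A mixed model fitted to the combined score in effect predicts a living non-responder from a distribution that includes the zeros of the dead, although that person cannot have a zero by death. Multiple imputation has the same fault if the zeros are in its data and vital status is not handled. Linear regression on available data and the complete-case analysis take the bias in full.

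At stake are the level and time course of a secondary outcome in both randomized comparisons. Under some conditions the arm contrasts are affected as well.

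**Working it through.** **The plan's own figure.** No calculation in the plan concerns EQ-5D. The only one is the primary-outcome sample size, from "an annual event rate of 14 per 100 participant years", a 12% relative reduction and "80% power, allocation ratio of 1:1, average follow up of 3 years". The Poisson-regression formula gives (1.960×2 + 0.842×√(2 + 1/0.44))² / (0.14×3×(ln 0.88)²) ≈ 4667, and ×1.01 = 4714, as stated. This neither supports nor weakens the point.

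**Inputs for EQ-5D.** From the documents: waves at 6, 18 and 33 months; 4768 randomized (7.1), so about 2384 per level of each intervention; death = 0. Assumed: living mean 0.80, cumulative deaths *d*, response among the living *r*. The 26% three-year composite risk in 4.8 includes death, so it caps *d* in the source cohort.

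**Step 1: available data.** Share of zeros s = d/(d + (1−d)r). Relative weight of the dead w = s/d. Bias = −0.80(s − d).

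| d | r | s | w | available mean | target 0.80(1−d) | bias |
|---|---|---|---|---|---|---|
| 0.10 | 0.65 | 0.100/0.685 = 0.146 | 1.46 | 0.683 | 0.720 | −0.037 |
| 0.05 | 0.65 | 0.050/0.6675 = 0.075 | 1.50 | 0.740 | 0.760 | −0.020 |

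**Step 2: mixed model.** Simulation with SD 0.17, within-person correlation 0.6, 65% response at 33 months and unstructured covariance gave a 33-month mean about 0.024 to 0.028 too low with 10% dead, and 0.014 to 0.016 too low with 5% dead. A separate simulation (SD 0.15, response 90/80/70% by wave, 2384 per level, 30 runs) gave:

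- 5.5% dead: −0.017 in available data, −0.011 in the mixed model.
- 11% dead: −0.032 in available data, −0.019 in the mixed model.

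In that simulation the mixed model removes about 40% of the bias.

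**Step 3: growth by wave.** Take deaths of 1%, 3% and 5.5%, in available data.

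- Constant 80% response: w = 1.25, 1.24, 1.23, so the relative over-weighting is flat. Bias still grows: −0.002, −0.006, −0.010.
- Response 90/80/70%: w = 1.11, 1.24, 1.40. Bias −0.001, −0.006, −0.017.

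**Step 4: arm contrast.**

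- Equal deaths and equal response: no bias.
- Deaths 5% v 6%, response 70% in both: s = 0.0699 v 0.0836. A real 0.80×0.01 = 0.008 becomes 0.80×0.0136 = 0.011 in available data.
- No true effect, 10% dead, response 60% v 70%: s = 0.156 v 0.137, a false 0.80×0.0193 = 0.015 in available data and about 0.009 (intermittent non-response) to 0.011 (monotone dropout) in the mixed model.
- The same with 5% dead: 0.80×(0.0806 − 0.0699) = 0.009 in available data and about 0.006 in the mixed model.
- In the separate simulation, response 75% v 65% gave 0.008 (11% dead) and 0.005 (5.5% dead) in the mixed model.

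**Step 5: scale.** In those last two scenarios the Monte Carlo errors of the mean difference over 30 runs were 0.0015 and 0.0012. Multiplying by √30 gives standard errors of about 0.0082 and 0.0066 for one trial. The false differences are then roughly 1.0 and 0.8 standard errors. With "We will consider our alpha value to be 0.05", taken as two-sided, such shifts would raise the rejection rate under no effect to about 16% and 12%. Thirty runs make this rough.

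**Step 6: does reordering help?** Modelling the living first and inserting zeros afterwards brought the 33-month mean to within about 0.0004 of target under the first set of assumptions. In the separate simulation a residual of −0.002 to −0.004 remained, with false arm differences of 0.001 or less.

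**The case against.** **Death = 0 is intended.** This stands, and the convention is not challenged. A reader might infer that the whole decline in mean EQ-5D is an artefact. It is not: with full response and 5.5% dead the mean still falls from 0.80 to 0.756. Only the excess is bias.

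**The plan does not simply drop living non-responders.** This stands in part. A mixed model uses a person's other waves, and 9.1, 10.3 and 6.3 plan imputation. None of them conditions on vital status, so the bias is reduced but remains.

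**One planned analysis largely escapes.** LOCF gives a living non-responder the last living score, never a death zero. Its 33-month bias was about 0.000 in simulations where survivors' scores do not decline. It is secondary, and that condition is not assured.

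**No rates are given.** This is correct. Two stronger readings are therefore unsupported: that the dead are over-weighted more at every wave, which needs falling response, and that the arms differ by construction, which needs deaths or response to differ by arm. Differential response is possible for the open-label education comparison but is not shown, and controls may also receive annual mailings (4.2). The education programme is balanced across the copayment arms, so it offers no reason for differential response in that comparison.

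**Larger error rates depend on the model.** A random-intercept, constant-variance fit rejected in 44% of simulated null trials (10% dead, response 60% v 70%). But it also rejected in 16% with equal response, which is a separate variance problem, and the plan specifies no such structure.

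**Exploratory status.** Section 5.2 treats secondary outcomes other than the components of the primary as exploratory. That limits the consequences but does not justify a biased estimate.

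**Conclusion.** The concern holds for the level of EQ-5D. Followed as written, 6.3 gives a mean below its own target whenever some participants have died and some survivors have not responded. The direction needs no assumed rates. The size does: about 0.024 to 0.028 at 33 months with 10% dead and 0.014 to 0.016 with 5% dead, under the values in Step 2. The bias grows as deaths accumulate.

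For the arm contrast the finding is conditional. With equal deaths and response there is no bias. A real mortality difference is magnified, and unequal response among survivors creates a false difference of the order of one standard error under the assumptions shown. The documents do not establish that either condition occurred.

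The primary outcome is not affected. The change should be made, because a better order of steps exists and uses data the plan already obtains.

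**What to change.** Keep death = 0 and change the order of the analysis in 6.3:

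1. Fit the mixed model or multiple imputation only to person-waves at which the participant is alive, with death zeros left out of the model data.
2. Predict missing scores person by person, only for those known to be alive in Alberta at that wave. The fitted wave means should not be used directly, since they describe a cohort in which nobody dies. State a rule for the few who left the province and whose vital status is unknown.
3. Insert 0 for those dead at that wave. Compare arm means at 6, 18 and 33 months over all randomized participants, with Rubin's-rules or bootstrap intervals.
4. Use the same order for the multiple-imputation area-under-curve analysis.
5. Report by arm and wave the proportion alive, response among the living, and the mean score among the living.
6. Show the 10.9 complete-case result for the living only, or weight responding survivors up to all survivors.
7. Reconcile the mixed model in 6.3 with the linear regression in 10.5.

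The cost is revised wording, some programming and possibly slightly wider intervals. No new data are needed beyond survey scores and administrative dates of death and outmigration. The later SAP's introduction says that main trial findings have been reported. If EQ-5D has been analysed too, which that introduction does not say, the cost is a re-analysis.

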7.2. Baseline Characteristics

Baseline characteristics will be reported in a Table using descriptive summary statistics. These will be stratified by group assignment, and t-tests/Chi2 tests will be used to examine for inter-group differences in these characteristics.

8. Data Sources

The main data source for the trial will be the ACCESS trial RedCAP database. This contains participant group assignments and all patient reported measures from baseline, 6-month, 18-month, and 33-month surveys. It also contains individuals' unique provincial health number which will permit deterministic linkage to administrative health databases held by Alberta Health (including Alberta Precision Laboratory data, Pharmacy Information Network Data, Practitioner Claims data, Discharge Abstract Database, National Ambulatory Care Reporting System data). All PHNs were verified at the time of study enrollment to be sure that they were accurate and active. In cases where a deterministic linkage is not possible, probabilistic linkage using name, date of birth, and postal code will be used.

9. Interventions (s)

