10.5. Analysis Methods- Secondary Outcomes

Medication adherence is a binary variable and will be analyzed using log binomial regression (generalized linear models with a log link)—given the likely high prevalence of non-adherence.

EQ5D index scores are continuous and will be analyzed using linear regression.

Medication self-efficacy and concerns will be dichotomized and analyzed using logistic regression.

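### Both EQ-5D missing-data checks compare an area under the curve, not the mixed-model score contrast, so a difference from the main result cannot be put down to missing data alone

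*Combined protocol and SAP*

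**What the plan says.** All references are to the combined protocol and SAP.

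Section 6.3 gives the main EQ-5D analysis: "Mixed models will be used to compare EQ-5D index scores over time between the treatment groups for each intervention". It does not say which contrast the model will report (an average over visits, the final visit, a slope, or a joint test).

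It then states the purpose of the further analyses: "In secondary analyses of EQ-5D index scores, to assess the impact of missing data, we will consider two alternate methods using imputation". After multiple imputation, "We will then use this data to compare the area under the curve of index scores across each intervention group". For the other method, "Secondly, we will use last observation carried forward to impute missing values, and then similarly compare the area under the curve of index scores". The section concludes: "Both approaches will test the impact of missingness of data".

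Other sections bear on the point:

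- Section 8 lists "all patient reported measures from baseline, 6-month, 18-month, and 33-month surveys", which sets the time points for an AUC.
- Section 9.1 uses multiple imputation for patient-reported outcomes after withdrawal.
- Section 10.3 allows multiple imputation or direct maximum likelihood under missing at random (MAR), with sensitivity analyses for data missing not at random (MNAR) if MAR is doubtful.
- Section 10.9 plans a complete case analysis for self-reported outcomes.
- Section 10.5 describes the main model differently: "EQ5D index scores are continuous and will be analyzed using linear regression".

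Sections 9.1, 10.3 and 10.9 do not say which EQ-5D quantity they would use.

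**The concern.** A missing-data sensitivity analysis is informative when only the handling of missing data changes. Here the main result is a contrast of index scores, while each check is a contrast of AUCs after imputation. Section 6.3 plans neither an AUC from the mixed model nor a mixed-model contrast refitted to imputed data, so the bridge between the two is absent.

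If a check differs from the main result, the cause may be the missing data, the change of quantity, or both. If they agree, two influences may have offset each other. Quality of life is a named secondary outcome (Section 4.4), and Section 10.3 expects that missing self-reported data may be considerable. Readers will therefore lean on these checks.

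**Working it through.** The plan gives no EQ-5D effect size, standard deviation or missing-data rate, so there is no figure of its own to reproduce. The useful question is whether the two quantities can differ when nothing is missing.

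**Inputs.** Survey times are 0, 6, 18 and 33 months (Section 8). The intervals are 6, 12 and 15 months.

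**AUC weights.** Under the trapezoid rule each visit receives half of each adjoining interval. Dividing by 33 gives a time average:

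- baseline: (6/2)/33 = 3/33 = 0.091
- 6 months: (6/2 + 12/2)/33 = 9/33 = 0.273
- 18 months: (12/2 + 15/2)/33 = 13.5/33 = 0.409
- 33 months: (15/2)/33 = 7.5/33 = 0.227

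Multiplying the time average by 33/12 = 2.75 years gives QALYs. An equal-weight average of the post-baseline visits uses weights 0, 1/3, 1/3, 1/3. A final-visit contrast uses 0, 0, 0, 1.

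**Complete data, peak effect set to 1.** The effect shapes are illustrative.

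| Effect at 0, 6, 18, 33 months | AUC/33 | Visit average | Final visit | AUC against average | AUC against final |
|---|---|---|---|---|---|
| Constant: 0, 1, 1, 1 | 0.909 | 1.000 | 1.000 | 9% lower | 9% lower |
| Linear: 0, 6/33, 18/33, 1 | 0.500 | 0.576 | 1.000 | 13% lower | 50% lower |
| 33 months only: 0, 0, 0, 1 | 0.227 | 0.333 | 1.000 | 32% lower | 77% lower |
| 6 months only: 0, 1, 0, 0 | 0.273 | 0.333 | 0 | 18% lower | final visit shows no effect |

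For example, in the third row 1 − 0.227/0.333 = 0.32 and 1 − 0.227/1 = 0.77.

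**Effect on significance.** Complete data were simulated 20,000 times per scenario. The number per side of each factor was 4768/2 = 2384, from the number randomized in Section 7.1 and an assumed even split. The other assumptions are not in the documents: SD 0.20, equal correlation between visits of 0.5 or 0.7, peak difference 0.02, and a two-sided 5% test. The share of runs in which significance differed from the AUC result was:

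| Effect shape | Visit average | Final visit | Slope |
|---|---|---|---|
| Constant | 1–3% | 5–6% | 10–22% |
| Linear | 11–12% | 36–44% | 43–50% |
| 33 months only | 11–13% | 77–80% | 80–86% |

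The ranges cover the two correlations. All of this disagreement arises with no data missing.

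**Holding the quantity fixed.** With complete data, the AUC contrast is exactly the weighted sum of the visit-mean differences. On a simulated data set, the direct AUC difference and the weighted sum were both 0.01133. Once the same quantity is used throughout, the artefact disappears.

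**The case against.** The strongest reply is that the plan contains more missing-data work than Section 6.3 suggests. Multiple imputation after withdrawal (9.1) and the general rule for self-reported outcomes (10.3) may already feed the main EQ-5D analysis. The complete case analysis (10.9) could supply a like-for-like comparison, and the conditional MNAR work (10.3) could do so too. This stands in part: it softens the consequence. It does not repair Section 6.3, because none of these sections names the EQ-5D quantity.

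A reader might go further and infer that the checks say nothing about missing data. The documents do not support that. The two imputed AUC analyses use the same quantity, so the difference between them does show sensitivity to the imputation method. Only the comparison of either one with the mixed-model result mixes two changes.

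A reader might also infer that multiple imputation merely repeats the mixed model's MAR assumption. That need not be so. MAR is conditional on the variables used, and Section 10.3 plans to bring in predictors of loss to follow-up. If the imputation model has them and the mixed model does not, the assumptions differ.

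Finally, 77% should not be read as the expected discrepancy. It requires an effect at the last survey only and a final-visit contrast, and the plan commits to neither. For a constant effect the gap is about 9%.

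The two descriptions of the main model do not rescue the checks. Section 10.5 names linear regression, but still of index scores and not of AUC.

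**Conclusion.** The concern holds for the comparison that matters most, that of each check with the main EQ-5D result. As written, a difference cannot be attributed to missing data alone, and agreement is weak evidence that missing data do not matter. The closing claim of Section 6.3 is therefore stronger than the design supports, although the comparison between the two imputations remains valid.

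The shift produced by changing the quantity alone depends on the mixed-model contrast, which is unspecified, and on how the effect develops over time. Where the compared contrast is not zero, it runs from about 9% to 77% across the shapes examined. The percentages rest on the survey schedule and the trapezoid rule. The significance figures rest also on the assumed SD, correlations and effect size.

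The consequence is limited. EQ-5D is a secondary outcome, and Section 5.2 treats secondary outcomes other than the components of the primary endpoint as exploratory. The primary result and the sample size are untouched.

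**What to change.** In Section 6.3, name one EQ-5D contrast and hold it fixed across the missing-data methods. Either route works:

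1. Refit the same mixed-model contrast on the multiply imputed, carried-forward and complete-case data.
2. Derive the AUC contrast from the mixed model with weights 0.091, 0.273, 0.409 and 0.227 (times 2.75 for QALYs), and compare it with the imputed AUC results. Treat baseline in the same way in both.

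If neither is wanted, report AUC as a separate QALY summary and remove the statement that it tests missingness. In each case, state in Sections 10.3 and 10.9 which EQ-5D quantity is used, and bring Section 10.5 into line with Section 6.3 on the main model. The rule in Section 6.3 that after a death "subsequent index scores will be given a score of 0" should apply in the same way to every version compared.

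An MNAR shift analysis on the same contrast is optional, with shift values chosen and justified by the trial team.

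The cost is a few sentences and a few extra model runs. No new data are needed.
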